5. PATIENT SELECTION CRITERIA

Patient population should be selected without bias.

Investigator(s) must keep a record of patients who entered pre-trial screening but were never enrolled eg, patient screening log. Each patient must meet all of the inclusion criteria and none of the exclusion criteria for this study. Under no circumstances can there be exceptions to this rule.

5.1 Inclusion criteria

For inclusion in the study patients must fulfil the following criteria.

1. Provision of informed consent prior to any study specific procedures

2. Male, or female of non-child bearing potential (defined as amenorrhoeic for 12 months and follicle stimulating hormone (FSH) plasma concentration within the post-menopausal range as defined by the laboratory) or surgically sterile (defined as having undergone bilateral oophrectomy and/or hysterectomy; tubal ligation on its own is not adequate), between 18 and 80 years
3. Have a clinical diagnosis of idiopathic or post infective bronchiectasis as diagnosed with a historical high resolution computerised tomography (HRCT) or bronchogram
4. Be sputum producers with a history of chronic expectoration on most days of most weeks of the year. Patients should have a history of spontaneously producing an average of 3 ml or more sputum on a daily basis and should be able to provide at least 2 of the 3 required baseline sputum samples
5. Have normal laboratory values at Visit 1, unless the investigator considers an abnormality to be clinically irrelevant

5.2 Exclusion criteria

Patients must not enter the study if any of the following exclusion criteria are fulfilled

1. Involvement in the planning and/or conduct of the study (applies to both AstraZeneca staff and/or staff at the study site)
2. Previous randomization of treatment in the present study
3. Participation (defined as administration of at least one dose of investigational product) in another clinical study within 12 weeks of Visit 1.
4. Bronchiectasis associated with a generalised immunodeficiency disorder, where manifestations other than bronchiectasis predominate
5. Concomitant diagnosis of significant pulmonary disease other than bronchiectasis or COPD, including symptomatic asthma and allergic bronchopulmonary aspergillosis
6. An FEV₁ of <30% of predicted normal at Visit 1
7. Any ECG abnormality at Visit 1 (including a QTc interval of >450 msec for males and >470 msec for females, or any arrhythmia) which in the opinion of the investigator may put the patient at risk or interfere with study assessments.
8. An acute exacerbation (defined as an increase in respiratory symptoms requiring hospitalisation and/or a course of oral glucocorticosteroids and/or antibiotics, either prescribed or self administered); or acute respiratory infection (upper or lower) requiring oral steroids or antibiotics in the 6 weeks prior to Visit 2

9. Other acute infections requiring treatment in the 4 weeks prior to Visit 2
10. Use of prohibited medications as detailed in Section 6.5
11. A past history of or current clinical or laboratory evidence of renal disease, or a calculated creatinine clearance (Cockcroft-Gault formula) of ≤ 70 ml/min at Visit 1
12. Any other clinical disease or disorder (including insulin dependent diabetes) which, in the opinion of the investigator, may either put the patient at risk because of participation in the study, or may influence the results of the study, or the patient's ability to participate in the study
13. History of excessive alcohol consumption or chronic alcohol induced disease
14. Donation of >1350 mL of blood in the 12 months or 500 mL of blood in the 3 months before the end of the study
15. Suspected or known risk of the patient transmitting HIV, Hepatitis B or C
16. Scheduled in patient surgery or hospitalisation during the course of the study

Criteria relating specifically to the optional pharmacogenetics component can be found in Appendix D.

5.3 Procedures for handling incorrectly included patients

Patients that do not meet the inclusion/exclusion criteria for a study should not, under any circumstances, be enrolled into the study – there can be no exceptions to this rule.

Where patients that do not meet the study criteria are enrolled in error, incorrectly randomised, or where patients subsequently fail to meet the criteria for the study post enrolment, the procedures included in the protocol for the discontinuation of such patients must be followed. These procedures must be included in the protocol and must take into consideration ethical and safety factors and how these patients will be treated in the analyses.

Once the error is identified a discussion must occur between the AZ Study Team Physician and the Investigator regarding whether to continue or discontinue the patient from the study. The AZ Study Team Physician is to ensure all such decisions are appropriately documented. In situations where an agreement cannot be reached, the patient should have their randomised therapy stopped and be discontinued from the study.

5.4 Withdrawal of patients

5.4.1 Criteria for discontinuation from the study

Patients may be discontinued from study treatment and assessments at any time. Specific reasons for discontinuing a patient are:

- Voluntary discontinuation by the patient who is at any time free to discontinue his/her participation in the study, without prejudice to further treatment
- Risk to patients as judged by the investigator and/or AstraZeneca
- Severe non-compliance to protocol as judged by the investigator and/or AstraZeneca
- Incorrectly enrolled patients
- Patient lost to follow-up
- Non-compliance to study medication (compliance rate of $\leq 80\%$ following drug accountability at Visit 3)
- Change in QTc >60 msec from baseline value or QTc >500 msec, confirmed by repeat ECG
- Withdrawal of informed consent to the use of biological samples **collected as an integral part of the study**, see Section 8.5
- An ALT / AST level $\geq 3 \times \text{ULN}$ (confirmed on repeat sample) or any pattern of liver function test (LFT) abnormalities giving Investigator or AZ cause for concern
- Evidence of haemolysis as evidenced by the following:
 - Reticulocyte count of over 5%, **and**At least two of the following:
 - a drop in haemoglobin below 10.5 g/dL
 - decrease of 25% in haptoglobin. (The value post-dose to be compared with the average of two pre-dose values. The value should also be 15% below LLN).
 - increase of 25% in unconjugated bilirubin or lactate dehydrogenase (LDH). (The value post-dose to be compared with the average of two pre-dose values. The value should also be 15% above ULN).
- A platelet count of below $80 \times 10^9/\text{L}$ confirmed by a repeat test (in the absence of obvious platelet clumping in a peripheral blood film).

Specific reasons for discontinuing a patient from the genetic research are detailed in Appendix D:

- Withdrawal of consent for genetics research. A patient may withdraw from this genetic research at any time, independent of any decision concerning participation in other aspects of the main study described in this protocol. Voluntary discontinuation by the patient will not prejudice further treatment.

5.4.2 Procedures for discontinuation of a patient from the study

A patient that discontinues will always be asked about the reason(s) for discontinuation and the presence of any adverse events. If possible, they will be seen and assessed by an investigator(s). Adverse events will be followed up (See Sections 7.3.3 and 7.3.4); diary cards and study drug should be returned by the patient.

If a patient discontinues they should be asked to attend the follow up visit (Visit 5).

6. STUDY CONDUCT

6.1 Restrictions during the study

1. Use of disallowed concomitant medication (refer to Section 6.5).
2. Patients should not donate blood at any time during the study or for 3 months following completion of the study
3. Patients should fast from the midnight (00:00) prior to dosing until 2 hours post-dose on clinic days where ECGs are being performed, ie, Days 1 (Visit 2) and 28 (Visit 4). Water is allowed up to 1 hour before drug administration and will be allowed from 2 hours after drug administration.
4. Patients should abstain from taking part in any other study, whilst participating in this study.
5. Male patients should abstain from unprotected sex and sperm donation from date of consent until 3 months after last dosing. Recommended contraception will be double barrier method, ie, condom and in addition, the female partner to use a reliable contraceptive method, or they must refrain from sexual intercourse for the same time period.
6. There is no evidence from clinical experience to date that AZD9668 is capable of inducing photosensitivity. However until further studies are concluded, patients should be advised not to sunbathe or use sunbeds or U-V lamps, and to limit exposure to sunlight as much as practicable during dosing and for 1 week after last dose of study medication.

6.2 Patient enrolment and randomization

The principal investigator will:

1. Obtain signed informed consent from the potential patient before any study specific procedures are performed.
2. Assign potential patient a unique enrolment number, beginning with “E0001001 (EXXXYYYY)” where XXXX reflects the centre number and YYY will be allocated sequentially to enrolled patients at each centre.
3. Determine patient eligibility. See Sections 5.1 and 5.2
4. Assign eligible patient unique randomization code (patient number), beginning with “001”.

Randomisation codes will be computer generated by AstraZeneca R&D using the AstraZeneca Global Randomisation System (GRand). Patients who are withdrawn for any reason other than adverse events will be replaced as the aim is to achieve 40 evaluable patients. Randomization numbers should not be re-used.

Randomization codes will be assigned strictly sequentially as patients are eligible for randomization (Visit 2).

If a patient discontinues participation in the study, then his/her enrolment/randomization code cannot be reused.

If patients have discontinued after randomisation into the study then they cannot re-enter into the study.

6.2.1 Procedures for randomization

Biostatistics will be responsible for producing the randomisation code in GRand. There will be no formal stratification.

6.3 Blinding and procedures for unblinding the study

6.3.1 Methods for ensuring blinding

AZD9668 will be provided as a tablet for oral administration and with a matching placebo. Tablets of AZD9668 will be provided in the strength of 30 mg.

6.3.2 Methods for unblinding the study

Code break envelopes will be sent to site with drug supplies.

Individual treatment codes, indicating the treatment randomization for each randomised patient, will be available to the investigator(s) or pharmacists at the study centre.

A copy of the randomisation scheme will also be made available to the analyst of AZD9668 in sputum and the PK plasma analyst, to enable the analysis of samples from patients who have received active treatment to be prioritised. This documentation will be placed in a secure location until the end of the study.

A copy of the treatment codes will also be supplied to the Scottish poisons bureau (for use in the event of an out of hours medical emergency in the UK) and the Canadian patient safety group (for use in the event of an out of hours medical emergency in Canada).

The treatment code must not be broken except in medical emergencies when the appropriate management of the patient necessitates knowledge of the treatment randomization. If the treatment code is broken then the investigator(s) must document and report to AstraZeneca.

AstraZeneca retains the right to break the code for SAEs that are unexpected and are suspected to be causally related to an investigational product and that potentially require expedited reporting to regulatory authorities. Treatment codes will not be broken for the planned analyses of data until all decisions on the evaluability of the data from each individual patient have been made and documented.

There is no planned interim analysis.

6.4 Treatments

6.4.1 Identity of investigational product(s)

Table 5 Identity of investigational products

Investigational product	Dosage form and strength	Manufacturer	Formulation number *
AZD9668	Tablet 30 mg	AstraZeneca R&D, [REDACTED]	1756 / H 2029-01-01
Placebo AZD9668	Tablet	AstraZeneca R&D, [REDACTED]	P1756 / H 2030-01-01

* The batch number will be detailed in the CSR (Clinical Study Report)

The composition of the tablets is 30 mg AZD9668 (corresponding to 39.5 mg AZD9668 tosylate).

Excipients: cellulose microcrystalline, calcium hydrogen phosphate dihydrate, crospovidone, sodium laurilsulfate, sodium stearyl fumarate.

The drug product consists of white to off white, plain oblong, biconvex tablet. The nominal tablet weight is 400 mg.

Placebo tablets to match AZD9668 tablets contain the following excipients: cellulose microcrystalline and sodium stearyl fumarate.

Tablets will be supplied (at Visit 2 then again at Visit 3) in bottles containing 72 tablets, which is sufficient for 14 days+/-2 days dosing b.i.d plus overage.

6.4.2 Doses and treatment regimens

Patients will be advised to fast from midnight (00:00) prior to Visit 2 (Day 1) where they will be randomised to receive either AZD9668 tablets 60 mg or placebo tablets (using a 1:1 randomisation scheme) orally twice daily for 28 days (± 2 days). The first dose will be administered, with 100mL water, in the clinic in the morning of Day 1.

The patients will be issued with sufficient tablets to allow self-dosing until Visit 3.

At Visit 3 (Day 14 ± 2 days) patients will attend the clinic in the morning. There is no requirement to withhold their morning dose.

The patients will be issued with sufficient tablets to allow self-dosing until Visit 4.

At Visit 4 (Day 28 ± 2 days) patients will be advised to fast from midnight (00:00) and attend the clinic in the morning, having withheld taking their dose of study medication for that day. Patients will take their last dose(s) of study medication in the clinic with 100mL water. There will only be one dose administered on this final day.

There is no requirement for the patients to fast around dosing at any other point during the study.

6.4.3 Additional study drug

No additional study drug will be provided for this study.

6.4.4 Labelling

The packaging and labelling will be performed by [REDACTED]. All supplies and labels will be prepared in accordance with Good Manufacturing Practice (GMP) and local regulatory guidelines.

The labels will fulfil GMP Annex 13 requirements for labelling.

The bottles will be labelled with a two-panel label. One part of the label will be permanently affixed to the bottle and the other part will be a peel-off part for insertion into the CRF at the time of administration.

The boxes, containing 2 bottles, will be labelled with a single-panel label without tear-off part.

The label will include at least the following information:

- Name of sponsor (AstraZeneca)
- Study drug(s) dosage form, route of administration and quantity of dosage units

- Study code
- Enrolment code or Randomisation code
- Directions for use
- Expires end
- For clinical trial use only
- Keep out of the reach of children

6.4.5 Storage

All study drugs must be kept in a secure place under appropriate storage conditions. The investigational product label on the bottle and boxes of study drug specifies the appropriate storage requirements.

6.5 Concomitant and post-study treatment(s)

Patients are allowed to continue long-acting muscarinic antagonists (LAMA), long-acting beta agonists (LABA), LABA/ICS (inhaled corticosteroids) combinations unchanged throughout the study if they are already on these.

They would only need to withhold LAMA/LABA for 12 hours, short-acting beta agonists (SABA) for 6 hours and short acting muscarinic antagonists (SAMA) for 8 hours before their pulmonary function tests. After they have had the test they could take their normal dose of the medication.

In addition, the following treatments are not allowed:

- Use of oral corticosteroids in the 8 weeks prior to Visit 2 and throughout the study (N.B. use of inhaled corticosteroids is allowed)
- Use of non-prophylactic antibiotics, systemic or nebuliser, in the 4 weeks prior to Visit 2 and throughout the study (N.B. prophylactic use is allowed)
- Treatment with immunomodulatory agents within 8 weeks prior to Visit 2 and throughout the study

As AZD9668 is a CYP2C9 inhibitor, the following drugs which are CYP2C9 substrates, will not be allowed throughout the dosing period (ie, Visit 2 - 4):

- Anti-diabetics/hypoglycaemics
- Anti epileptics/anticonvulsives
- Warfarin

- Fluvastatin
- Celecoxib
- High dose, continuous NSAIDs; documented PRN use is allowed. Ibuprofen is permitted only at low to medium doses (<20 mg/kg/day)
- Torsemide
- Amitryptiline
- Fluoxetine

Any other drugs including inhaled and oral respiratory drugs could be allowed provided their doses have been stable for at least 4 weeks before enrolment and the doses remain unchanged throughout the study. SABA and/or SAMA may be taken as needed for symptomatic control of breathlessness.

Other medication which is considered necessary for the patient's safety and well-being, may be given at the discretion of the investigator and should be recorded in the pCRF.

Please refer to 6.1 for other restrictions during the study.

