4.2 Rationale for study design, doses and control groups

The rationale for conducting this study in patients with bronchiectasis and the rationale for dosing up to 28 days are given in Section 2.3. A parallel group rather than a cross over design is considered more appropriate, as the possible duration of effect is uncertain and therefore a carry-over cannot be completely eliminated. The rationale for dose selection is given below.

The first-in-man, two-part, single and multiple ascending dose (SAD and MAD) study of AZD9668 in healthy volunteers (D0520C00001) is now complete and the reporting phase is underway. In the SAD part of the study the doses that have been safely administered were 2, 10, 30, 60, 120 and 150 mg. Dose escalation was stopped because the exposure limits set by the internal AstraZeneca Human Exposure Limits Committee (HELIC) were reached. These limits (i.e. $AUC_{(0-24h)}$ and C_{max} of 18 $\mu M \cdot h$ and 2.5 μM , respectively) were set following a review of the data obtained in the 1-month toxicology studies in the rat and dog and have been based upon the exposures at the no observed adverse effect level (NOAEL) in rat (370 mg/kg), corrected for the differences in plasma protein binding between the species. The NOAEL in the rat has been used because the free exposures at this dose are lower than those obtained in the dog at the no observed effect level (NOEL) dose. In the MAD part of the study the doses that have been safely administered were 30, 70 and 120 mg once a day for a total of 8 days.

Following single dose administration of AZD9668 (2 - 150 mg) absorption was rapid, median t_{max} ranged from 1 to 2 hours. The geometric mean CL/F ranged from 15.4 to 21.6 L/h and the geometric mean V_z/F ranged from 157 to 334 L. The geometric mean terminal half-life of AZD9668 ranged from 5.04 to 14.99 h. The CL/F, V_z/F and $t_{1/2}$ appeared to be independent of dose. The exposure (C_{max} and AUC) increased proportionally with dose between doses of 10 mg and 150 mg.

AZD9668 is renally eliminated and renal clearance (CL_R) and the percentage of the dose excreted as unchanged AZD9668 in the urine over 48 h ($F_{e(0-48)}$ (%)) appeared to be independent of dose. The geometric mean CL_R ranged from 5.83 L/h to 6.98 L/h, and the range of the geometric mean $F_{e(0-48)}$ (%) was 31.6% to 40.0%.

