Following multiple dose administration of AZD9668 (30 mg, 70 mg and 120 mg, once a day for 8 days), absorption was similar following single and multiple dosing; the median t_{max} and $t_{max,ss}$ was 1 hour for all dose groups. The geometric mean $CL/F_{,ss}$ was 14.7, 14.8 and 19.4 L/h and the geometric mean $V_z/F_{,ss}$ was 191L, 218 and 245L, respectively. The geometric mean $t_{1/2,ss}$ was 9.04 hours, 10.24 hours and 8.73 hours, respectively, and there was no evidence for time or dose dependent change in PK. There was no evidence of accumulation upon multiple dosing to steady state.

AZD9668 is renally eliminated and renal clearance at steady state ($CL_{R,ss}$) and the percentage of the dose excreted as unchanged AZD9668 in the urine at steady state over 48 hours ($F_{e(0-48),ss}$ (% dose)) appeared to be independent of dose. The geometric mean $CL_{R,ss}$ was 5.29 L/h, 5.70 L/h and 5.83 L/h, and the geometric mean $F_{e(0-48),ss}$ (% dose) was 38.8%, 40.9% and 31.6%, respectively.

Administration of AZD9668 after consumption of a high fat meal resulted in a reduction in the rate of absorption (median t_{max} was 4 h, 3 h and 4 h for 30 mg, 70 mg and 120 mg, respectively). The C_{max} was reduced by 22 %, 31 % and 22 % and the $AUC_{(0-24h)}$ was slightly reduced, by 8%, 5% and 5% for 30 mg, 70 mg and 120 mg, respectively. Thus consumption of the food reduced the rate but had relatively little effect on the overall extent of absorption.

A population PK model of the PK data from the SAD and MAD study has been developed and was used to estimate the mean population PK parameters of AZD9668 with the associated variability and to assess the affect of consumption of a high fat breakfast on the PK of AZD9668. A dose of 60 mg twice a day has been selected as the dose for the current study. This dose has been chosen as a dose that is predicted to achieve trough steady state therapeutic plasma concentrations of 19 nM (predicted from an in vivo mouse acute lung injury model) in all patients, whilst ensuring that the predicted geometric mean $C_{max,ss}$ and $AUC_{(0-24h),ss}$ are below the HELC limits. The estimated margins to the HELC limits in the fasted state are 2.6 and 1.4 for $C_{max,ss}$ and $AUC_{(0-24h),ss}$, respectively.

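### The section 6.5 ban on CYP2C9 substrates ends at Visit 4, the day of the last dose, with no washout (minor patient-safety point)

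*Protocol*

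**What the plan says.** All references are to the protocol.

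- **Section 6.5** names CYP2C9 inhibition by AZD9668 as the reason for the ban. The listed drugs are those "which are CYP2C9 substrates, will not be allowed throughout the dosing period (ie, Visit 2 - 4"). They include warfarin, anti-epileptics and hypoglycaemics. NSAIDs are treated more leniently: the entry reads "High dose, continuous NSAIDs; documented PRN use is allowed", and ibuprofen is permitted below 20 mg/kg/day.
- **Section 6.4.2** places the final dose at Visit 4, on a morning attendance: "Patients will take their last dose(s) of study medication in the clinic with 100mL water". Only one dose is given that day.
- **Section 5.2, exclusion 10** bars entry for "Use of prohibited medications as detailed in Section 6.5".
- **Section 6.1, item 6** does carry a drug-related precaution past the last dose. Patients are "to limit exposure to sunlight as much as practicable during dosing and for 1 week after last dose of study medication".
- **Section 4.2** gives the steady-state half-life for 30, 70 and 120 mg once daily: it "was 9.04 hours, 10.24 hours and 8.73 hours, respectively, and there was no evidence for time or dose dependent change in PK". After single doses, the geometric mean terminal half-life ranged from 5.04 to 14.99 h.
- **Table 3** puts Visit 5 at 7 days (±2) after Visit 4.

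**The concern.** The ban rests on a property of the study drug, so it should last about as long as the drug is present in a relevant amount. It is tied instead to the dosing period, and its last day is a day on which a full dose is taken. Section 6.5 covers post-study as well as concomitant treatment, so a post-dose rule belongs there and would not normally be left to a statistical analysis plan.

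At stake is the safety of a patient on active drug (about 20 of the 40 randomised) who starts or resumes a listed drug in the first two or three days after the last dose. The entries that matter most are those with no on-treatment allowance, such as warfarin, anti-epileptics and hypoglycaemics. The Visit 2 to Visit 4 limit also fits early stoppers poorly: they may have no Visit 4, and section 5.4.2 asks them only to attend Visit 5.

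**Working it through.** **Inputs (section 4.2).** Steady-state half-lives 9.04, 10.24 and 8.73 h; CL/F,ss 14.7, 14.8 and 19.4 L/h; Vz/F,ss 191, 218 and 245 L; single-dose half-lives 5.04 to 14.99 h. All are dose-group geometric means in healthy volunteers. No half-life is given for 60 mg twice daily in patients.

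**Step 1: reproduce the stated half-lives.** Half-life = ln 2 × (Vz/F) ÷ (CL/F).

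- 30 mg: 0.693 × 191 ÷ 14.7 = 9.01 h (stated 9.04)
- 70 mg: 0.693 × 218 ÷ 14.8 = 10.21 h (stated 10.24)
- 120 mg: 0.693 × 245 ÷ 19.4 = 8.75 h (stated 8.73)

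The figures agree.

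**Step 2: level after the last dose, relative to the usual trough.** At steady state on twice-daily dosing, the level 12 h after the last dose is the usual trough. Assume simple exponential decline from there. At t hours after the dose, the ratio to trough is 0.5^((t − 12) ÷ half-life). At 24 h and a half-life of 8.73 h, for example, 0.5^(12 ÷ 8.73) = 0.386.

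| Half-life (h) | 24 h | 36 h | 48 h | Five half-lives (h) |
|---|---|---|---|---|
| 5.04 (single dose, shortest) | 19.2% | 3.7% | 0.7% | 25.2 |
| 8.73 (steady state) | 38.6% | 14.9% | 5.7% | 43.7 |
| 9.04 (steady state) | 39.8% | 15.9% | 6.3% | 45.2 |
| 10.24 (steady state) | 44.4% | 19.7% | 8.7% | 51.2 |
| 14.99 (single dose, longest) | 57.4% | 33.0% | 18.9% | 75.0 |

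**Step 3: the same level relative to peak, for scale.** Section 4.2 sets limits of 2.5 µM for Cmax and 18 µM·h for AUC(0-24), and gives margins to them: "The estimated margins to the HELC limits in the fasted state are 2.6 and 1.4 for" Cmax,ss and AUC(0-24),ss respectively.

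- Predicted Cmax,ss = 2.5 ÷ 2.6 = 0.96 µM.
- Predicted AUC(0-24),ss = 18 ÷ 1.4 = 12.86 µM·h, or 6.43 µM·h per 12-h interval.
- Solving 0.96 × (1 − exp(−12k)) ÷ k = 6.43 gives k = 0.109 per hour, so the 12-h trough is about 27% of peak. This ignores the absorption phase.
- At 24 h, the steady-state half-lives give 27% × 38.6-44.4% = about 10-12% of peak.

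**Step 4: how long an extension has to be.** Three days (72 h) falls just short of the 75 h that five half-lives take at 14.99 h. Four days (96 h) is 96 ÷ 14.99 = 6.4 half-lives at that value. At 120 h, the earliest Visit 5 for a completer, the level is 0.5^(108 ÷ half-life) of trough: 0.02-0.07% at the steady-state half-lives and 0.7% at 14.99 h.

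**The case against.** The strongest reply is that the gap is largely closed by other rules. Exclusion 10 keeps current users out. Section 6.5 also admits other drugs only if the dose was settled for four weeks before enrolment and does not change during the study. If a listed drug falls under that rule once the specific ban lapses, a new start after Visit 4 would need the investigator's judgement that it is necessary. Adverse events, concomitant medication and safety bloods are checked at Visit 5.

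Part of this stands. Exclusion 10 makes affected patients few, and Visit 5 helps detection, though not prevention. The stable-dose rule does not cure the gap. It is written for drugs other than those listed, and the listed drugs have their own express time limit. Exclusion 10 itself points back to section 6.5, which bars these drugs only from Visit 2. A patient who paused one beforehand could therefore be eligible, and Visit 4 is the natural time to resume.

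A second reply is that harm is not shown. That is correct. The figures above are concentrations, not degrees of enzyme inhibition. The protocol gives no inhibition constant, section 6.5 tolerates some NSAID overlap at full exposure, and interaction detail may be in the Investigator's Brochure, which is not at hand.

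A third is that the sunlight rule is a poor comparator. It is a provisional precaution for a different hazard, so its longer duration shows only that the protocol can extend a precaution past dosing. It is not evidence of an inconsistency.

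**Conclusion.** The point holds as a minor, precautionary one. A ban justified by the drug's own enzyme inhibition has a poorly chosen end. About 24 h after the last dose, the level is still 39-44% of the usual trough at the steady-state half-lives, or 19-57% across the single-dose range. Clearance by the five-half-life convention takes 44-51 h, or 25-75 h. This assumes exponential decline from 12 h, that volunteer group means carry over to these patients, and that the ban covers all of Visit 4 day.

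Three stronger readings are not supported:

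- **Full on-treatment exposure after the ban.** A reader might infer that the listed drugs are allowed alongside a whole dosing interval's exposure (6.43 µM·h). That follows only if the ban stops at the hour of the last dose, which the wording does not require.
- **A contradiction.** Sections 6.4.2 and 6.5 are consistent with each other. The end point is weak, not contradictory.
- **A demonstrated interaction or an effect on results.** The size of any interaction cannot be computed from the protocol. The primary comparisons in section 12.2 use treatment-period data up to Visit 4, so no endpoint, sample size or analysis changes.

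**What to change.** In section 6.5, replace the Visit 2 to Visit 4 limit on the CYP2C9 list with: *from Visit 2 until Visit 5 (for patients who stop early, until at least 4 days after the last dose of study medication)*. Keep the existing investigator discretion for medication needed for the patient's safety and well-being.

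Visit 5 is an existing visit and needs no new procedure. Tying the rule for early stoppers to the last dose covers those with no Visit 4.

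The cost is one phrase in the protocol. Patients who want a listed drug wait about 5-9 more days after Visit 4, unless the investigator judges it necessary sooner.
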